2.3.1 Primary Endpoint

The primary endpoint is the composite measure of all-cause death, myocardial infarction (MI) or stroke (modified Rankin Scale (mRS) ≥ 1 and increase by ≥ 1 from baseline). measured by the Kaplan-Meier failure rate estimate at 3 years. For the primary analysis of the primary endpoint, this Kaplan-Meier rate will be defined from the date of randomization. All available data through 3-year follow-up will be used, but only events occurring up to day 1095 after randomization will be counted for the primary endpoint. For a sensitivity analysis, the Kaplan-Meier rate will be defined at the time of the index procedure date. Both of these analyses will be conducted at the time when approximately 50% of the patients have reached the 3-year follow-up AND all patients have reached the 2-year follow-up, whichever time point is latest.

For the primary and sensitivity analyses, days from the randomization date and procedure date to the first occurrence of one of the events within this composite, an early withdrawal date, or the last follow-up date will be calculated for each patient respectively. For patients who dropped out early, but had a death date available per the national death registry, this date will be used in the calculation of days (and will be counted as a primary endpoint event). If a patient does not have an event or an early withdrawal date:

- Days from randomization will be set to 1095 days (3 years) if their last follow-up date is known to occur after 3 years.
- The date of the last visit will be the date of the last phone call, office visit or medical contact.

The primary endpoint will first be tested for noninferiority with a margin of 4.2%. The critical value will be generated using the Com-Nougue¹ approach to estimating the Z-statistic with Greenwood's formula for estimating the standard error.

$$Z = \frac{F_{CABG}(T) - F_{PCI}(T) - \delta}{\sqrt{Var(F_{CABG}(T)) + Var(F_{PCI}(T))}}$$

Where, for each treatment group (CABG or PCI):

F(T) = Kaplan Meier estimator of failure at time T

 δ = non-inferiority margin

Var = variance of the estimator = σ^2 , where σ is defined as:

$$\sigma$$
 = standard error by Greenwood's formula = S(T=1095) $\sqrt{\sum_{j=1}^{1095} \frac{d_j}{n_j s_j}}$

S = 1 - F = KM estimate of survival at time T

n = number of subjects

d = number of events

s = n-d

The 95% CI for $F_{CABG}(T) - F_{PCI}(T)$ is then:

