$$F_{CABG}(T) - F_{PCI}(T) \pm \mathbf{z}_{1-\alpha} \sqrt{Var(F_{CABG}(T)) + Var(F_{PCI}(T))}$$

P-value = 1- probnorm(Z)

Superiority testing of the primary endpoint will be performed using the same Z-statistic calculation that is defined above, without the non-inferiority margin. Statistical significance will be evaluated for both analyses at a 1-sided alpha level of 0.025.

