2.5.1 Primary Endpoint

The primary endpoint of all cause death, MI or stroke (mRS \geq 1 and increase by \geq 1 from baseline) occurring up to 3 years post randomization will be evaluated using the difference in Kaplan-Meier failure rates in the intent-to-treat population. For the primary endpoint, sample size calculations for the Com-Nougue approach¹, which utilizes the difference in Kaplan-Meier failure rate estimates, were derived using simulations. The Com-Nougue approach was very similar to that calculated using the asymptotic approach (difference \leq 0.5%). Therefore, the asymptotic test was used to approximate the power for the Com-Nougue approach using PASS 2008 (NCSS, LLC. Kaysville, Utah)³.

The hypothesis test is designed to show non-inferiority of PCI to CABG for the primary endpoint via the Z statistic, which is a normal approximation to the Binomial, with a one-sided alpha of 0.025. The null (H_0) and alternative (H_A) hypotheses are:

```
H0: F_{PCI-PE}(T) - F_{CABG-PE}(T) \ge \Delta_{PE}
```

```
HA: F_{PCI-PE}(T) - F_{CABG-PE}(T) < \Delta_{PE}.
```

 F_{PCI-PE} and $F_{CABG-PE}$ are the Kaplan-Meier estimates of failure rate of the primary endpoint at 3 years in the PCI and CABG arms, respectively. Δ_{PE} is the non-inferiority margin for the primary endpoint.

The sample size calculation is based on the following assumptions:

- primary endpoint event rate is 11% in each treatment arm at 3 years (using 3-year event rates from the SYNTAX trial, the most contemporary reference dataset)
- minimum time to follow-up is 2 years
- median time to follow-up is approximately 3 years
- 8% lost to follow-up at 3 years
- non-inferiority margin $\Delta_{\text{PE}} = 4.2\%$
- one-sided alpha = 0.025
- accrual time of 29 months.

A sample size of 1,900 subjects (950 per arm) will provide approximately 80% power to

demonstrate non-inferiority of PCI to CABG.

If non-inferiority is met, superiority testing will be performed with a one-sided alpha of 0.025. The null (H_0) and alternative (H_A) hypotheses for the superiority test are:

H₀: $F_{PCI-PE}(T) - F_{CABG-PE}(T) \ge 0$

H_A: $F_{PCI-PE}(T) - F_{CABG-PE}(T) < 0$.

Using a one-sided alpha of 0.025, assuming 8% lost to follow-up at 3 years, the trial will have approximately 80% power to demonstrate superiority with a difference of 3.84% of PCI to CABG (e.g. 7.16% in the PCI arm vs. 11% in the CABG arm).

2.5.2 Major Powered Secondary Endpoints:

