3.2 Analysis of the Primary Endpoint

The primary analysis for non-inferiority and superiority will use the Kaplan-Meier estimates defined from randomization date. A sensitivity analyses for superiority will also be performed where time is defined from randomization. Additional sensitivity analysis for the same non-inferiority and superiority test mentioned above will be rerun changing the start date from randomization to procedure date. The stop date for all analyses defined at 3 yeatrs will be 1095 days from randomization.

Primary and supplemental analyses are defined below.

- 1. Primary Analysis of the Primary Endpoint for non-inferiority: Code for the primary analysis testing for non-inferiority with 1-sided alpha = 0.025, the non-inferiority margin $\delta = 4.2\%$.
 - Run the product-limit model:

```
Proc lifetest data = DATAXX method = pl cs=none atrisk
```

```
timelist = 1095 outsurv = OUTSURV ;
```

Time Timevar*Censvar(0);

strata/ Group = treatment test = logrank;

Run;

- Use results in OUTSURV to compute formula in 2.3.1. Reject Ho if the critical value $< -Z_{1-\alpha}$
- 2. Primary Analysis of the Primary endpoint using Z test for Superiority: Code for the primary endpoint testing for superiority with 1-sided alpha = 0.025: same as above, only use $\delta = 0$ in calculations. This will be the primary test for superiority.
- 3. Sensitivity Analysis using Cox Model for Superiority: The primary endpoint is tested for superiority with 1-sided alpha = 0.05 using a Cox proportional hazards model. The proportional hazard assumption will first be tested by plotting the log-negative-log survival curves vs the log of survival time for each level of treatment group.

If it is determined that the proportional hazard assumption is violated, then a logistic regression will be performed adjusting for time of follow-up in each group.

Code to Test Proportional Hazard Assumption:

proc lifetest data=DATAXX plot=(lls) noprint; time Timevar*Eventvar(0); strata Group; run; Code for Cox model where Proportion Hazard Assumption is **Not** violated: ods output ParameterEstimates=*Out1*; Proc phreg data = DATAXX ; model Timevar*Eventvar (0) = Group / rl; run;

Summary tables for time to event endpoints will include failure rates (Kaplan-Meier estimates), unadjusted hazard ratios, confidence interval for the hazard ratio, and a p-value.

```
Code for Logistic Regression used when Proportional Hazard Assumption is violated:

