proc logistic data= DATAXX descending;

class Group;

model Event (event=1) =TimeVar Group / rl;

run;

Where Event = all first events from randomization or procedure date to 1095 days

Timevar = Days from Randomization or procedure date to last data point

available for patient while on study. If the patient did not drop

out prior to the analysis time point then this will be set to the

analysis time point.
```

The odds ratio, 95% confidence interval of the odds ratio and p-value will be presented from this logistic model

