3.10 MULTIPLICITY ISSUES

If EXCEL has met the primary analyses of its primary endpoint of the non-inferiority test on the ITT population, additional hypothesis tests for the of the powered secondary endpoints based on the ITT population will be performed following a fixed sequence as below (FWER=family wise error rate). All of these analyses will be performed from time from randomization:

Step 1: Family 1. Primary Endpoint: Death/MI/Stroke at 3 Years PCI non-inferior to CABG (one-sided alpha of 0.025) If passed non-inferiority, PROCEED to Step 2
If failed non-inferiority, STOP

Step 2: Family 2. Major Secondary Endpoint 1: Death/MI/Stroke at 30 Days PCI non-inferior to CABG

(one-sided alpha of 0.05)

If passed non-inferiority, PROCEED to Step 3
If failed non-inferiority, STOP

Step 3: (Simultaneous Testing of 3-1 and 3-2) 3-1. Family 1. Primary Endpoint: Death/MI/Stroke at 3 Years PCI superior to CABG (one-sided alpha of 0.025) 3-2. Family 3. Major Secondary Endpoint 2: Death/MI/Stroke/Revascularization at 3 Years PCI non-inferior to CABG

(one-sided alpha of 0.05)

For hypothesis test(s) of each of the major powered secondary endpoints, the type I error is a 1sided alpha of 0.05. If any hypothesis testing fails in steps 1 and 2, no further testing for the following step will be performed for labeling purposes. However they will still be tested for research and publication purposes. For example, if PCI failed to show non-inferiority to CABG for the major power secondary endpoint of Death/MI/Stroke at 30 Days (step 2), then the hypothesis in step 3 will not be tested for labeling purposes, but may be tested for exploratory reasons. Caution must be exercised when interpreting p-values displayed for analyses other than those performed for the primary and key powered secondary endpoints, as the study was not powered to detect differences on any of those other variables. The resulting p-values, whether or not less-than 0.05, may be a result simply due to chance, and are displayed for hypothesisgenerating purposes only.

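### SAP 3.2 runs the Cox sensitivity test for superiority at one-sided 0.05 rather than 0.025, and its logistic fallback ignores administrative censoring

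*SAP*

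**What the plan says.** **Significance level.** SAP 3.2 item 3 sets the Cox sensitivity analysis as follows: "The primary endpoint is tested for superiority with 1-sided alpha = 0.05 using a Cox proportional hazards model". Four other places give the level for superiority of the same endpoint:

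- SAP 2.3.1, on the non-inferiority and superiority Z tests: "Statistical significance will be evaluated for both analyses at a 1-sided alpha level of 0.025".
- SAP 2.5.1: "If non-inferiority is met, superiority testing will be performed with a one-sided alpha of 0.025".
- SAP 3.2 item 2: "Code for the primary endpoint testing for superiority with 1-sided alpha = 0.025: same as above".
- SAP 3.10 step 3-1: "Death/MI/Stroke at 3 Years PCI superior to CABG (one-sided alpha of 0.025".

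**Fallback.** If the log-log plot leads to the judgement that the "proportional hazard assumption is violated, then a logistic regression will be performed adjusting for time of follow-up in each group". The outcome is any first event up to day 1095. For a patient who did not drop "out prior to the analysis time point then this will be set to the" analysis time point, here 1095 days. SAP 2.3.1 is stricter for the primary analysis: "Days from randomization will be set to 1095 days (3 years) if their last follow-up date is known to occur after 3 years". SAP 3.8 and 3.4.3 likewise censor at the last assessment. SAP 3.7 triggers the analysis when about half the patients have reached 3 years and all have reached 2. SAP 3.6.1.3 repeats the logistic fallback for its adjusted models.

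**The concern.** A sensitivity analysis should ask at least as much as the test it supports. At one-sided 0.05 the Cox test can report superiority when its own two-sided 95% interval includes 1, so agreement with the primary test would say less than it appears to.

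The fallback has a different problem. A patient at 2.3 years at data cut-off, event-free and still on study, has not dropped out and so enters as a full 3-year non-event. Events that such patients would have had later are missed. If the arms have the same 3-year risk but one has its events earlier, fewer of that arm's events are missed, and the odds ratio leans toward the arm with later events. Unequal timing is one form of non-proportional hazards, the condition that triggers the fallback. SAP 2.6 itself expects lower peri-procedural morbidity with PCI, so earlier events under CABG are plausible.

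**Working it through.** **1. Which level the design uses.** Inputs from SAP 2.5.1: 7.16% vs 11%, 950 per arm, 8% lost, stated power about 80%.

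- n = 950 × 0.92 = 874 per arm.
- SE = √(0.0716×0.9284/874 + 0.11×0.89/874) = 0.01371, and 0.0384/0.01371 = 2.80.
- At one-sided 0.025: Φ(2.80 − 1.960) = 80.0%, which reproduces the stated figure.
- At one-sided 0.05: Φ(2.80 − 1.645) = 87.6%, which does not.

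The design level for superiority is therefore 0.025.

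**2. What the looser level means for the Cox test.** The largest hazard ratio declared superior is exp(−2z/√D), where D is the number of events.

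| D | one-sided 0.05 | one-sided 0.025 |
|---|---|---|
| 193 | 0.789 | 0.754 |
| 198 | 0.792 | 0.757 |
| 158.7 | 0.770 | 0.733 |

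The range 193 to 198 is what step 4 implies with 11% in both arms. The value 158.7 = 874 × (0.0716 + 0.11) applies at the planned superiority effect. The gap between the two levels is about 0.035 to 0.04 throughout.

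**3. How many patients the fallback miscounts.** With 29 months of accrual (SAP 2.5.1; uniform accrual is an assumption) and a 24-month minimum, 12/29 = 41% are under 36 months at the analysis. In simulation with 8% withdrawal by 3 years, about 35% of all patients are event-free, on study and counted as complete.

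**4. Bias when 3-year risks are equal.** Assumptions:

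- 950 per arm, with 11% risk at 3 years in each arm.
- Administrative censoring uniform over days 730 to 1612.
- Exponential withdrawal reaching 8% by day 1095.
- Early events uniform over days 0 to 30, later events uniform over days 30 to 1095.

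Integrating the probability of still being under observation gives P(observed) = 0.9989 for an early event and 0.8925 for a late one. The observed proportion in an arm is 0.9989 × early + 0.8925 × late. For 8%+3% in CABG this is 0.0799 + 0.0268 = 10.67%. For 3%+8% in PCI it is 0.0300 + 0.0714 = 10.14%. The odds ratio is (0.1014/0.8986)/(0.1067/0.8933) = 0.945, and ln OR = −0.057. The standard error is √[1/(950×0.1067×0.8933) + 1/(950×0.1014×0.8986)] = 0.150. One-sided rejection at 0.025 is then Φ(−1.96 + 0.057/0.150) = 5.7%.

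| By day 30 + later, CABG vs PCI | Observed, CABG vs PCI | OR | Rejection at 0.025 | Rejection at 0.05 |
|---|---|---|---|---|
| 8%+3% vs 3%+8% | 10.67% vs 10.14% | 0.945 | 5.7% | 10.3% |
| 6%+5% vs 3%+8% | 10.46% vs 10.14% | 0.966 | 4.2% | 7.8% |
| 4%+7% vs 2%+9% | 10.24% vs 10.03% | 0.977 | 3.5% | 6.8% |
| 3.5%+7.5% vs 2.5%+8.5% | 10.19% vs 10.08% | 0.988 | 3.0% | 5.8% |
| equal timing | 10.14% in both | 1.00 | 2.5% | 5.0% |

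Rows three and four have 30-day rates averaging the 3% planned in SAP 2.5.2.

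**5. Does the time covariate help?** In a simulation of 1.5 million patients per arm, the odds ratio in row one was 0.945 without the covariate, 0.945 with it as written, and 0.946 with it recoded to last follow-up. All five scenarios agree within about 0.001. The cause is the unweighted binary outcome, so recoding the covariate does not repair it.

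**6. Does the primary method have the same problem?** In 8,000 simulated trials the Kaplan-Meier difference at day 1095 rejected in 2.3%, 2.5% and 2.7% of trials in rows one to three, with Monte Carlo error of about 0.2 points.

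**The case against.** The Cox test sits outside study success (SAP 2.7) and the testing sequence (SAP 3.10), and the hazard ratio, interval and p-value reported would be the same whatever threshold is named. The 0.05 may be a slip for two-sided 0.05. The fallback reports a 95% interval for the odds ratio, which implies one-sided 0.025 even though no level is stated for it. SAP 3.8 and 3.4.3 were not written for this logistic model. All of this is fair. It limits the consequence but does not explain two levels for one hypothesis.

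On the bias, the larger figures rest on 30-day rates well away from the planned 3% per arm; near the plan, rejection is only 3.0% to 3.5%. SAP 2.3 also starts the adverse event check at day 758 for the last patient. A 758-day minimum leaves 38% short of 3 years, with odds ratios of 0.950, 0.969, 0.979 and 0.990 and rejection of 5.3%, 4.0%, 3.4% and 2.9%. The bias is slightly smaller and the pattern is the same. Read literally, the 50% trigger would allow more censoring, not less.

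Finally, falling back on the Kaplan-Meier difference leaves no separate model-based check when hazards are non-proportional. That is true. But SAP 3.2 also reruns the tests from the procedure date, SAP 2.4 adds per-protocol and as-treated analyses, and a censoring-weighted model remains available. A biased check is not a useful substitute.

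**Conclusion.** Both parts hold. The level in item 3 contradicts four other statements in the SAP and doubles the nominal one-sided error of that test from 2.5% to 5%. The fallback is biased toward the arm with later events: none under equal timing, an odds ratio of about 0.98 to 0.99 when 30-day rates stay near the plan, and about 0.945 in the most extreme scenario examined. These sizes rest on uniform accrual, 8% withdrawal in each arm and the assumed event timing. The documents do not show how likely the fallback is to be used. Only supporting and exploratory analyses are affected. The point should be corrected but does not threaten the primary conclusion.

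**What to change.** 1. In SAP 3.2 item 3, set the level to one-sided 0.025 (two-sided 0.05) and state that any fallback uses the same level.
2. Delete the logistic fallback and its code. If hazards are judged non-proportional, rely on the Kaplan-Meier difference at day 1095 in item 2, which handles both censoring and non-proportionality. If an odds ratio is still wanted, fit logistic regression at day 1095 with inverse-probability-of-censoring weights estimated by arm, robust standard errors and no time covariate. Note that it will largely restate the Kaplan-Meier estimates.
3. In SAP 3.6.1.3, make the same change for the two 3-year outcomes, using the weighted model if an adjusted odds ratio is needed. Leave the 30-day model alone: every patient has reached 2 years, so none is administratively censored by day 30.

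The cost is one number, one deleted paragraph with its code, and one matching edit. The optional weighted model also needs a censoring model by arm. Data collection, timing, sample size, the primary tests, study success and the testing sequence stay as they are.

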3.3 Analysis of the Powered Secondary Endpoints

- The first powered secondary endpoints, the KM estimate of the composite rate of allcause mortality, MI or stroke (mRS≥1 and increase by ≥1 from baseline) from randomization to 30 days post randomization, will be analyzed in a similar fashion as the primary analysis of the primary endpoint described in Section 3.2 above. The key differences are that a 1-sided alpha is set at 0.05 and only non-inferiority will be tested at a margin of 2%.
- The second powered secondary endpoint is the KM estimate of the composite rate of all cause mortality, MI, stroke (mRS≥1 and increase by ≥1 from baseline) or unplanned revascularization at 3 years. The same analysis will be performed as described for the primary anaylsis of the primary endpoint except the non-inferiority margin = 8.4%

3.4 Analysis of the Secondary Endpoints (Not powered)

All non-powered secondary endpoints will use a 2-sided alpha of 0.05.

3.4.1 Continuous Variables

For continuous variables (e.g., age, percent diameter stenosis, and lesion length), results within treatment arm will be summarized with the numbers of observations, means, medians, standard deviations, 25th and 75th percentiles, minimums, and maximums per the table mockups. Differences between the treatment arms, where specified, will be summarized with the differences of the two means, 95% confidence intervals for the difference between the means, and p-values based on a t-test. The distributions within each group will be tested for normality using the Shapiro-Wilks test and if normality cannot be assumed then a Wilcoxon rank-sum test and 95% confidence interval of the median will be presented. The confidence interval for the difference of two means will be calculated under the assumption of unequal variances.

Formulas for calculation of the confidence intervals for the continuous variables are given below:

 100(1-α)% Confidence Interval For The Difference of Two Means Under The Assumption of Unequal Variances Between The Two Groups⁵

$$(\overline{x}_1 - \overline{x}_2) \pm t_{\frac{\alpha}{2}} SED$$

With the degrees of freedom for the approximate t statistic is determined by Satterthwaite's formula³ as follows:

$$df = \frac{\left(w_1 + w_2\right)^2}{\frac{w_1^2}{n_1 - 1} + \frac{w_2^2}{n_2 - 1}}$$

where:

 $\overline{x}_1 =$ samplemean for group1

 $\overline{x}_2 = \text{samplemean for group 2}$

 $s_1 =$ samplestandarddeviation for group1

 $s_2 =$ samplestandarddeviation for group 2

 $n_1 = \text{sample size for group 1}$

 $n_2 = \text{sample size for group } 2$

$$\text{SED} = \sqrt{\frac{{s_1}^2}{n_1} + \frac{{s_2}^2}{n_2}}$$

$$w_1 = \frac{{s_1}^2}{n_1}$$
$$w_2 = \frac{{s_2}^2}{n_2}$$

3.4.2 Categorical Variables

For categorical variables such as gender, in-hospital event rates, and angina status, results within treatment arm will be summarized with subject counts and percentages. Differences between the two treatment arms, where specified, will be summarized with the difference in percentages, the asymptotic 95% confidence interval for the difference of two percentages, and a p-value based on a chi-squared test. If 20% or more of the expected cell frequencies are less than 5 then a Fisher's Exact test will be used to test for differences in proportions.

For the determination of event rates in-hospital, the number of all subjects in the patient patient population will be used as the denominator. For variables ascertained at follow-up such as angina status, the denominator will be only those subjects who had follow-up performed at that time point. Unless otherwise noted, subjects with missing data are excluded from the denominator.

For secondary analyses of any type of death event for which event rates will be calculated, the denominator will include only subjects who have either had the event, died prior to the event time of interest, or had sufficient follow-up to be declared eligible for the endpoint. Sufficient follow-up implies that the subject had a follow-up visit past the lower limit of the window for the analysis time point (-7 days for the 30 day endpoint, and -30 days for yearly endpoints). Formulas for calculating confidence intervals for the categorical variables are given below. Please note that in using these formulas, it is assumed that the data are independent and binomially distributed. For the confidence interval for the difference of two proportions, it is also assumed that the two samples are independent, the samples sizes for the two groups are large (≥ 20 per group), the expected event and non-event counts for both groups are at least 5, and the distribution is asymptotically normal.

1. $100(1-\alpha)$ % Confidence Interval For The Difference Of Two Proportions⁶

Lower Confidence Limit =
$$(\hat{p}_1 - \hat{p}_2) - Z_{\frac{\alpha}{2}} \sqrt{\left(\frac{\hat{p}_1 \hat{q}_1}{n_1} + \frac{\hat{p}_2 \hat{q}_2}{n_2}\right) + \frac{1}{2} \left(\frac{1}{n_1} + \frac{1}{n_2}\right)}$$

Upper Confidence Limit = $(\hat{p}_1 - \hat{p}_2) + Z_{\frac{\alpha}{2}} \sqrt{\left(\frac{\hat{p}_1 \hat{q}_1}{n_1} + \frac{\hat{p}_2 \hat{q}_2}{n_2}\right) + \frac{1}{2} \left(\frac{1}{n_1} + \frac{1}{n_2}\right)}$

where:

| $\hat{p}_1 = \text{sample proportion for group 1}$ | $\hat{p}_2 =$ sample proportion for group 2 |
|---|---|
| $\hat{q}_1 = 1 - \hat{p}_1$ | $\hat{q}_2=1-\hat{p}_2$ |
| $n_1 = \text{sample size for group 1}$ | $n_2 = \text{sample size for group 2}$ |
| $Z_{\underline{\alpha}} = \text{the} (1 - \text{alpha}/2) Z - \text{statistic}$ | |
| 2 | |

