The first major powered secondary endpoint is defined as the composite of all cause death, MI, or stroke (mRS \geq 1 and increase by \geq 1 from baseline) occurring up to 30 days post randomization. It will be evaluated using the difference in Kaplan-Meier rates tested using the Com-Nougue approach¹ which is similar to the normal approximation to the binomial. The null (H₀) and alternative (H_A) hypotheses for non-inferiority of this major secondary endpoint is:

H₀: $F_{PCI-PE30}(T) - F_{CABG-PE30}(T) \ge \Delta_{PE30}$

H_A: $F_{PCI-PE30}(T) - F_{CABG-PE30}(T) < \Delta_{PE30.}$

 $F_{PCI-PE30}(T)$ - $F_{CABG-PE30}(T)$ is the difference in Kaplan-Meier rates at 30 days between PCI and CABG arms and Δ_{PE30} is the non-inferiority margin for this powered secondary endpoint.

The power calculation is based on the following assumptions:

- composite event rate is 3% in each treatment arm at 30 days
- non-inferiority margin $\Delta_{\text{PE30}} = 2\%$
- one-sided alpha = 0.05

A sample size of 1,900 subjects (950 per arm) will provide approximately 80% power to demonstrate non-inferiority of PCI to CABG.

The second major powered secondary endpoint is defined as the composite of all cause death, MI, stroke, or unplanned revascularization for ischemia occurring by 3 years post randomization. This composite will be evaluated using the difference in Kaplan-Meier failure rates at 3 years between CABG and PCI in all 3 patient populations. The hypothesis is designed to show non-inferiority of PCI to CABG with a one-sided alpha of 0.05. The null (H₀) and alternative (H_A) hypotheses for non-inferiority of this powered secondary endpoint are:

H₀: $F_{COMP-PCI}(T) - F_{COMP-CABG}(T) \ge \Delta_{COMP}$ H_A: $F_{COMP-PCI}(T) - F_{COMP-CABG}(T) < \Delta_{COMP}$. $F_{COMP-PCI}(T) - F_{COMP-CABG}(T)$ is the difference in failure rates at 3 years between CABG and PCI and Δ_{COMP} is the non-inferiority margin for this powered secondary endpoint.

The power calculation is based on the following assumptions:

- composite event rate is 22% in each treatment arm at 3 years
- minimum time to follow-up is 2 years
- median time to follow-up is approximately 3 years
- 8% lost to follow-up at 3 years
- non-inferiority margin $\Delta_{\text{COMP}} = 8.4\%$
- one-sided alpha = 0.05
- accrual time of 29 months

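### SAP 3.4.2 prints the interval for a difference of two proportions with the continuity correction under the square root, so the descriptive categorical intervals would be far too wide

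*SAP*

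**What the plan says.** SAP 3.4.2 covers categorical summaries: "For categorical variables such as gender, in-hospital event rates, and angina status". Where a between-arm difference is specified, the row shows the difference in percentages, the "asymptotic 95% confidence interval for the difference of two percentages", and a chi-squared p-value (Fisher's exact test when expected counts are sparse). For in-hospital rates, "the number of all subjects in the patient patient population will be used as the denominator". SAP 3.4 sets the level: "All non-powered secondary endpoints will use a 2-sided alpha of 0.05".

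The section then writes out the two limits separately, starting with the "Lower Confidence Limit". In ordinary notation both read

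(p1 − p2) ∓ Z · sqrt[ (p1q1/n1 + p2q2/n2) + (1/2)(1/n1 + 1/n2) ],

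with minus for the lower limit and plus for the upper. The section's own conditions are at least 20 subjects per group and expected event and non-event counts of at least 5.

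The main endpoints take another route. SAP 2.3.1, 2.3.2 and 3.4.3 use Kaplan-Meier estimates with Greenwood variances for the primary endpoint, the powered secondary endpoints and post-discharge time-to-event rates.

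**The concern.** The term (1/2)(1/n1 + 1/n2) is the usual continuity correction for a difference of two proportions. It is measured in units of a proportion and is added to Z times the standard error. Under the root it is treated as a variance. It then contributes 0.5 per observation, whereas a binomial variance p(1 − p) cannot exceed 0.25, so the correction outweighs the sampling variance it is meant to refine.

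A programmer who follows the text would report intervals labelled 95% that are much wider than that. The in-hospital comparisons are the ones most exposed. SAP 2.3.3 lists in-hospital death, stroke, revascularization and the major-adverse-event composite, and the margin justification in SAP 2.6 appeals to lower peri-procedural morbidity and fewer early strokes with PCI. Over-wide intervals would blur those early differences and could disagree with the p-value in the same row.

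**Working it through.** **Inputs.** n = 950 per arm: "A sample size of 1,900 subjects (950 per arm) will provide approximately 80% power to demonstrate non-inferiority of PCI to CABG" (SAP 2.5). Z = 1.96 from the two-sided 0.05 level. The SAP's planning rates are 3% ("composite event rate is 3% in each treatment arm at 30 days", SAP 2.5.2), 11% (SAP 2.5.1) and 22% (SAP 2.5.2). They serve here only as illustrative rates, with 1% and 50% added, because no in-hospital rate is given.

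**The plan's own figures.** No sample size or power rests on this formula. The stated power figures reproduce with the ordinary standard error sqrt(p1q1/n1 + p2q2/n2):
- 30-day endpoint (3%, margin 2%, one-sided 0.05, n = 950): SE = sqrt(2 × 0.03 × 0.97/950) = 0.00783; 0.02/0.00783 − 1.645 = 0.91; power 81.9%, against about 80% stated.
- Primary endpoint (11%, margin 4.2%, one-sided 0.025, n = 950 × 0.92 = 874): SE = 0.01497; 0.042/0.01497 − 1.96 = 0.85; power 80.1%, against about 80% stated.

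With the printed root as the standard error these would be 14.8% and 20.5%, so the plan's power was not computed that way. The only stated figure for the interval itself is its 95% level, tested below.

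**Half-widths at 950 per arm, equal rates.** The correction is c = 0.5 × (1/950 + 1/950) = 0.00105, or 0.105 percentage points.
- Correction outside the root: 1.96 × sqrt(2p(1 − p)/950) + c.
- As printed: 1.96 × sqrt(2p(1 − p)/950 + c).

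At 3%: outside, 1.96 × 0.00783 + 0.00105 = 1.64 points; printed, 1.96 × sqrt(0.0000613 + 0.0010526) = 6.54 points.

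| Rate | Outside root (points) | As printed (points) | Ratio |
|---|---|---|---|
| 1% | 1.00 | 6.42 | 6.4 |
| 3% | 1.64 | 6.54 | 4.0 |
| 11% | 2.92 | 6.95 | 2.4 |
| 22% | 3.83 | 7.37 | 1.9 |
| 50% | 4.60 | 7.79 | 1.7 |

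As p tends to zero the printed half-width tends to 1.96 × sqrt(0.0010526) = 6.36 points, which is its floor.

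**Coverage.** Exact binomial coverage at 950 per arm with equal true rates from 1% to 50%: without correction, 94.9% to 95.0%; with the correction outside the root, 95.4% to 97.5%; as printed, 99.93% at 50%, 99.99% at 22%, and above 99.999% at 11% and below.

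**Agreement with the paired test, 1% vs 3%.** Expected events are 9.5 and 28.5, within the section's conditions. The variance is (0.0099 + 0.0291)/950 = 0.00004105.
- Outside the root: half-width 1.96 × 0.00641 + 0.00105 = 1.36 points; interval −3.36 to −0.64.
- As printed: half-width 1.96 × sqrt(0.00004105 + 0.0010526) = 6.48 points; interval −8.48 to +4.48.
- Chi-squared with pooled rate 2%: z = 0.02/sqrt(2 × 0.02 × 0.98/950) = 3.11, p about 0.002.

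**If the root really ends after the binomial variances.** The lower limit becomes (p1 − p2) − Z·SE + c where it should be − c, an error of 2c = 0.21 points. The upper limit is then right.

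**The case against.** The strongest objection is that the finding depends on how far one radical sign extends in text taken from a PDF. The inner parentheses enclose only the two binomial variances, which is redundant if the root covers the whole sum and natural if it stops there. The subscript of Z beside the formula is visibly broken. One systematic misreading would affect both lines, so their agreement is weak evidence. This stands as a reason to check the source. It does not clear the formula: shortening the radical alone leaves the wrong sign in the lower limit. Both limits are right only if grouping braces were lost as well. Other radicals in the SAP (2.3.1, 3.4.1) show no sign of having been stretched.

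The second objection concerns consequence, and it largely stands. The error widens intervals and so cannot manufacture a difference. The p-values are computed separately. The SAP already urges caution outside the powered endpoints. Analyses run in SAS (SAP 3.12) and no code is printed for this formula, so the misprint may never reach the output.

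A reader might infer three stronger things that the documents do not support:
- That the primary or 30-day result is compromised. Both use Kaplan-Meier with Greenwood variance.
- That every between-arm interval is affected, including procedural factors. SAP 3.4.2 gives differences only where specified. Although SAP 4.2 speaks generally of differences for procedure information, the specific rule in SAP 4.2.7 bars comparisons of procedure and device data.
- That every interval contradicts its p-value. This happens only when a significant difference is smaller than the inflated half-width. At 950 per arm, differences beyond about 7.8 points still exclude zero.

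**Conclusion.** Wrong as written; minor to moderate severity. As the text reads, the formula does not give a 95% interval. At 950 per arm it is too wide by a factor of about 6.4 at a 1% rate, falling to 1.7 at 50%, and it can span zero beside a clearly significant chi-squared test. The factors assume equal rates in the two arms and full denominators of 950. The rates are illustrative, so no single multiple applies to the trial's in-hospital results.

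The reach is limited to descriptive between-arm categorical comparisons where the SAP calls for them: in-hospital event rates, angina status and baseline characteristics. The primary and powered secondary tests, post-discharge Kaplan-Meier rates, sample size and success rule are unaffected. The size depends on the radical being printed as it reads here. If only the radical was stretched, the error shrinks to 0.21 points in the lower limit.

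**What to change.** Check the extent of the radical and any braces in the source PDF. Then state the limits in SAP 3.4.2 as

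(p1 − p2) ∓ { Z · sqrt(p1q1/n1 + p2q2/n2) + (1/2)(1/n1 + 1/n2) },

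with the braces shown, so that the correction is subtracted in the lower limit and added in the upper. Dropping the correction is equally acceptable: at 950 per arm it is worth only 0.105 points on each side. The cost is one formula in the SAP and a check that the table programs match it. No data collection, sample size or hypothesis test changes.
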